## **6.8 Treatment after the end of the study**

Not applicable. This is a Phase 1 study in healthy participants; therefore, no treatment will be provided after the end of the study.

## **7 DISCONTINUATION OF STUDY MEDICATION AND PARTICIPANT DISCONTINUATION/WITHDRAWAL**

### **7.1 Discontinuation of study medication**

Events that may lead to discontinuation of study medication are described in Section 7.1.1 through Section 7.1.3.

#### **7.1.1 Hypersensitivity stopping criteria**

[figure not shown]
During the study, study participants will receive a [REDACTED] dose of investigational medicinal product (IMP) administered SC via a programmed syringe driver or by MP.

This will be performed under close and continued attention of the investigator or designee. In case of any signs of an infusion reaction or anaphylaxis, the infusion will be stopped immediately, and appropriate treatment will be initiated, as necessary, at the discretion of the investigator. This includes the use of antihistamines for urticaria and appropriate management in case of potentially life-threatening events such as anaphylaxis. Infusion may be restarted in mild reactions only if clinically appropriate. The study participant should be followed until resolution of the event. Rapid Alert procedure (Appendix 8 [Section 10.8]) should be followed, if indicated. See Appendix 12 (Section 10.12) and Appendix 13 (Section 10.13) for procedures to follow in the instance of infusion reactions and anaphylaxis, respectively.

#### **7.1.2 Liver chemistry stopping criteria**

The following liver chemistry stopping criteria for discontinuation of study medication do not apply (Figure 7-1). See Appendix 6 (Section 10.6) for procedures to follow in the instance of elevated liver function tests.

**Figure 7-1: Liver chemistry stopping algorithm**

ALT=alanine aminotransferase; AST=aspartate aminotransferase; INR=international normalized ratio; SAE=serious adverse event; ULN=upper limit of normal

Note: Suggested assessments and follow-up actions for potential drug-induced liver injury are provided in Appendix 6 (Section 10.6).

### 7.1.3 QTc stopping criteria

A participant who meets either bulleted criterion based on the ECG reading will be withdrawn from the study:

- QTcF >500msec
- Change from Baseline: QTcF >60msec

If a clinically significant finding is identified (including, but not limited to, changes from Baseline in QTcF interval after enrollment), the investigator or qualified designee will determine if the participant can continue in the study and if any change in participant management is needed. This review of the ECG printed at the time of collection must be documented. Any new clinically significant finding should be reported as an AE.

See Table 1-1 for data to be collected at the time of treatment discontinuation and follow up and for any further evaluations that need to be completed.

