i Vital signs will be measured predose and at 1, 2, 3, and 4 hours after the start of infusion and then prior to each PK sampling. Measurements will include blood pressure, pulse rate, respiratory rate, and tympanic body temperature. Vital signs and ECGs should be measured/taken before PK sampling, where applicable.

- Single 12-lead ECGs will be taken at Screening, Admission, predose, at 4, 12, and 24 hours after the start of infusion, and once a day on Days 3, 4, and 5 until discharge. All ECG recordings should be taken with the study participant resting in the supine position for at least 5 minutes before the recording.
- j Serology panel: Hepatitis B surface antigen, hepatitis B core antibody (both IgG and immunoglobulin M), hepatitis C virus antibody, and human immunodeficiency virus 1 and 2 antibody.
- k The PK sampling time points will be: predose, immediately at the end of infusion, 4, 6, 8, 12, 24, 36, 48, 72, and 96 hours after start of infusion, and on Days 7, 10, 13, and 16.
- l Dipstick urinalysis includes: pH, protein, glucose, ketone, urobilinogen, bilirubin, blood, nitrite, leukocytes; urine spot collections for albumin:creatinine ratio, total protein, albumin, creatinine, alpha-1 microglobulin, and beta-2 microglobulin; specific gravity; and microscopic examination (if blood or protein is abnormal).
- m Assessment of local tolerability of SC infusion (by the investigator or designee) will be completed predose, at the end of infusion, and 4, 6, 8, 12, 24, 36, 48, 72, and 96 hours after the start of infusion.
- n The SIAQ will be completed predose and 30 minutes to 1 hour postdose by study participants (MP cohorts only).
- o The ISRQ will be completed 30 minutes to 1 hour postdose by participants (syringe driver cohorts only).
- p Injection site pain VAS will be completed by all cohorts 30 minutes to 1 hour postdose.
- q Photographs of IMP injection site to be taken predose and 30 minutes after the end of the IMP administration, and additionally upon occurrence of any injection site reaction. An additional photograph will be taken if an injection site reaction occurs.

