- Cohort 4 (participants with a body weight of  $\geq 50$ kg) is planned to have 6 participants receive rozanolixizumab [REDACTED] and 2 participants receive placebo via MP through self-administration at a [REDACTED].

Since a [REDACTED] rozanolixizumab fixed dose has not been investigated thus far in lower weight (35 to 50kg) healthy participants, 2 sentinel study participants (1 active + 1 placebo) will be incorporated into Cohort 1 in order to collect safety and tolerability data over a 72-hour period. The SMC will convene to evaluate all available safety and tolerability data following completion of a 72-hour evaluation period and prior to staggered dosing of remaining participants in Cohort 1. As a further precautionary step for Cohort 1, dosing of the 6 post-sentinel participants will be staggered such that no more than 2 participants will be dosed in a 72-hour period with a

minimum of 48 hours between participants. In addition, the Rapid Alert process is in place throughout the study to ensure that exposure to the study medication is stopped if a reported event meets the stopping criteria (see Appendix 8 [Section 10.8]). Cohorts are not obliged to run in numerical sequence (ie, cohorts could run in parallel).

Since MP IMP administrations in this study will likely be at higher infusion rates than the [REDACTED] SC rate undertaken in all rozanolixizumab clinical studies to date, 2 sentinel study participants (1 active + 1 placebo) will be incorporated into Cohorts 2 and 4. Review of 48-hour postdose safety data by the SMC will enable dosing of the remaining participants (see Section 9.7 and Appendix 8 [Section 10.8]).

The eligibility of study participants will be determined during a Screening Period of up to 4 weeks (Day -28 to Day -2). Once eligibility is confirmed, the study participant will be admitted to the site (at Day -1 or the evening of Day -2) and will enter an In-Clinic Period through Day 5. Each study participant will receive a [REDACTED] SC dose of rozanolixizumab on Day 1 and may be discharged beginning at Day 5 at the discretion of the investigator. Each participant will only receive [REDACTED] IMP administration.

Beginning at Day 6, study participants will enter the Ambulatory Period and will attend the clinical site for study visits through Day 57 to allow sufficient time for systemic IgG levels to return to Baseline and for the assessment of anti-drug antibodies (ADAs).

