11. Bilirubin  $>1.0 \times \text{ULN}$  (isolated bilirubin  $<1.5 \times \text{ULN}$  is acceptable if bilirubin is fractionated and direct bilirubin  $<35\%$ ). Tests that result above the exclusion limit may be repeated once for confirmation.
12. Alanine transaminase (ALT), aspartate aminotransferase (AST), or alkaline phosphatase (ALP)  $>1.0 \times \text{ULN}$ . Tests that result in ALT, AST, or ALP up to 25% above the exclusion limit may be repeated once for confirmation. This includes rescreening. If the repeat values are below the ULN, the study participant will not be considered to have met the exclusion criteria.
13. Lymphoma, leukemia, or any malignancy within the past 5 years except for basal cell or squamous epithelial carcinomas of the skin that have been resected with no evidence of metastatic disease for 3 years.
14. Breast cancer within the past 10 years.
15. Absolute neutrophil count  $<1.5 \times 10^9/\text{L}$  and/or lymphocyte count  $<1.0 \times 10^9/\text{L}$ .
16. Corrected serum calcium of  $>11.5 \text{mg/dL}$  ( $>2.9 \text{mmol/L}$ ) or  $<8.0 \text{mg/dL}$  ( $<2.0 \text{mmol/L}$ ).
17. Predicted inability to comply with being free of caffeine and ethanol from 72 hours prior to clinic admission and during the In-Clinic Period of the study.

18. Known hypersensitivity to oral paracetamol (acetaminophen).
19. History of known inflammatory bowel disease, active diverticular disease, or a history of confirmed duodenal, gastric, or esophageal ulceration in the previous 6 months.
20. History of hyperprolinemia, since L-proline is a constituent of rozanolixizumab.
21. Twelve-lead ECG with abnormalities considered to be clinically significant upon medical review: male study participants with QT interval corrected for heart rate using Fridericia's formula (QTcF) >450msec and female study participants with QTcF >470msec, left bundle branch block, or evidence of myocardial ischemia.
22. Renal impairment, defined as a creatinine concentration in serum of  $\geq 1.4$ mg/dL ( $\geq 123$  $\mu$ mol/L) for female participants and  $\geq 1.5$ mg/dL ( $\geq 132$  $\mu$ mol/L) for male participants.

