## 7.2 Participant discontinuation/withdrawal from the study

Participants are free to withdraw from the study at any time, without prejudice to their continued care. The study is designed to collect data on 24 participants that receive rozanolixizumab (6 per cohort). If study participants discontinue before the end of the safety evaluation period, replacement participants may be considered at the discretion of the sponsor, depending on how the discontinuation affects the study's ability to collect sufficient data to support the study

objectives. For each case of participant discontinuation, the decision on whether to recruit a replacement and the reason behind the decision will be documented.

If the participant withdraws consent for disclosure of future information, the sponsor may retain and continue to use any data collected before such a withdrawal of consent.

If a participant withdraws from the study, he/she may request destruction of any samples taken and not tested, and the investigator must document this in the site study records. Participants who withdraw from the study will be encouraged to return to the clinic to complete the Withdrawal Visit (see [Table 1-1](#)).

See [Table 1-1](#) for data to be collected at the time of study discontinuation and follow-up and for any further evaluations that need to be completed.

Participants should be withdrawn from the study if any of the following events occur:

1. Participant develops an illness that would interfere with his/her continued participation.
2. Participant is noncompliant with the study procedures or medications in the opinion of the investigator.
3. Participant takes prohibited concomitant medications as defined in this protocol that might interfere with the outcome of the study or might be an increased risk to the study participant.
4. Participant withdraws his/her consent.
5. There is confirmation of a pregnancy during the study, as evidenced by a positive pregnancy test.
6. The sponsor or a regulatory agency requests withdrawal of the participant.

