### 8.9.1 Immunogenicity assessments

Immunogenicity testing will occur via a tiered analysis approach consisting of a Screening, confirmatory, and titration assay. Anti-drug antibodies to rozanolixizumab will be evaluated in plasma samples collected from all study participants according to [Table 1-1](#).

Additionally, for study participants withdrawing from the study an unscheduled sample should be taken for ADA analysis upon his/her last withdrawal visit. These samples will be tested by the sponsor or sponsor's designee.

Plasma samples with a "positive screen" result will enter a confirmatory ADA analysis whereupon addition of excess rozanolixizumab to the sample is performed in an attempt to immunodeplete the ADA signal. For samples with a "positive immunodepletion," an ADA titer will be determined.

The detection and characterization of antibodies to rozanolixizumab, vaccinations, and previous SARS-CoV-2 infections will be performed using a validated assay method under the supervision of the sponsor. Samples for ADA analysis may be stored for a maximum of 20 years (or according to local regulations) following the last participant's last visit for the study at a facility selected by the sponsor to enable further analysis of immune responses to rozanolixizumab.

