5.1.1.1.3 Mapping of assessments performed at Early Discontinuation Visit

Participants who withdraw from the study will be encouraged to return to the clinic to complete the Withdrawal Visit.

The following rules will apply regarding the inclusion of data obtained at the early discontinuation visit in the summaries and in the data listings:

- If the early discontinuation occurs at the time of the next scheduled visit, the results will be included with all other participants' results from that visit.
- If the early discontinuation visit does not correspond to the day of a scheduled visit, the results will be mapped to the nearest scheduled visit following the last scheduled visit where assessments were performed.

-
- If the date of the early discontinuation visit is equidistant between 2 scheduled visits at which no scheduled assessments were performed, the results from the withdrawal visit will be mapped to the earliest of these visits.

The results from the early discontinuation visit will be displayed as the mapped visit and will be flagged in the data listings.

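### For a post-dose trigger, the QTc rule in Protocol 7.1.3 requires withdrawal from the study, which withholds no dose and ends scheduled follow-up to Day 57

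*Protocol*

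**What the plan says.** Protocol 7.1 is headed as dealing with discontinuation of study medication and introduces 7.1.1 to 7.1.3 as events that may lead to it. Section 7.1.3 then goes further: "A participant who meets either bulleted criterion based on the ECG reading will be withdrawn from the study". The two limits are QTcF above 500 msec and a change from Baseline above 60 msec. Section 8.2.3 also calls them withdrawal criteria.

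The next paragraph of 7.1.3 deals with clinically significant findings, QTcF changes included, and says that "the investigator or qualified designee will determine if the participant can continue in the study". It does not say whether this discretion overrides the two limits.

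On dosing, Protocol 4.1 gives each participant a "SC dose of rozanolixizumab on Day 1 and may be discharged beginning at Day 5 at the discretion of the investigator". Table 1-1 has one administration cell, at hour 0. On ECG timing, the Table 1-1 footnote says: "Single 12-lead ECGs will be taken at Screening, Admission, predose, at 4, 12, and 24 hours after the start of infusion", then once daily on Days 3, 4 and 5. The ECG row of the table also marks Days 13 and 57.

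On what follows withdrawal, Protocol 7.2 says: "Participants who withdraw from the study will be encouraged to return to the clinic to complete the Withdrawal Visit". Section 8.9.1 adds that "for study participants withdrawing from the study an unscheduled sample should be taken for ADA analysis upon his/her last withdrawal visit". Under SAP 5.1.1.1.3, if that visit does not fall on a scheduled day, "the results will be mapped to the nearest scheduled visit following the last scheduled visit where assessments were performed".

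**The concern.** A QTc stopping rule normally protects a participant by preventing further exposure. Here the dose has already been given when the first scheduled post-dose ECG is taken at 4 h. Withdrawing the participant from the study then changes nothing about exposure. It only ends the visits that Protocol 4.1 extends to Day 57 so that IgG can return to Baseline and ADA can be assessed.

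Three things are at stake:

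- **Secondary PD endpoints.** The Baseline-corrected IgG AUC, the maximum decrease and its timing need samples over weeks, and SAP 5.1 does not impute missing data.
- **ADA status.** All post-dose sampling falls on Day 10 or later.
- **Other non-serious TEAEs.** Protocol 8.3.1 collects AEs up to the Safety Follow-Up or Withdrawal Visit. SAP 5.1 bases percentages on the number of participants, so someone observed for a few days counts the same as someone observed to Day 57. This is true of any dropout, but here the protocol itself imposes the dropout.

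**Working it through.** The plan states no figure to reproduce. The check is a reading of the rule against the dosing schedule, followed by a count of what remains in Table 1-1 after each trigger.

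**Step 1: can the rule withhold a dose?** Dosing is at hour 0 on Day 1. The word giving the number of administrations is redacted, so a single dosing occasion is inferred from the Day 1 text and the one cell in Table 1-1. Infusion duration is also redacted. The PK footnote lists the end of infusion before 4 h, so the 4 h ECG is taken to follow the end of infusion. On that basis no scheduled post-dose ECG can prevent exposure. The predose Day 1 ECG can, because it comes before the only dose.

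**Step 2: post-dose schedules.**

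- ECG, table row: 4, 12, 24, 48, 72 and 96 h, Days 13 and 57 = 8. ECG, footnote: 4, 12 and 24 h, Days 3, 4 and 5 = 6.
- Total IgG: 24, 48, 72 and 96 h, Days 7, 10, 13, 16, 19, 22, 29, 43 and 57 = 13.
- ADA, footnote u: Days 10, 16, 22 and 57 = 4.
- PK, footnote k: end of infusion, 4, 6, 8, 12, 24, 36, 48, 72 and 96 h, Days 7, 10, 13 and 16 = 14.
- Hematology: 24 h, Days 5, 10 and 57 = 4.
- Ambulatory visits: Days 7, 10, 13, 16, 19, 22, 29, 43 and 57 = 9.

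**Step 3: what remains after the trigger, and so is given up** (before any Withdrawal Visit; days = 57 − trigger day).

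| Trigger | Days | Visits (of 9) | Total IgG (of 13) | ADA (of 4) | PK, footnote (of 14) | Hematology (of 4) | ECG, row (of 8) | ECG, footnote (of 6) |
|---|---|---|---|---|---|---|---|---|
| 24 h (Day 2) | 55 | 9 | 12 | 4 | 8 | 3 | 5 | 3 |
| Day 5 | 52 | 9 | 9 | 4 | 4 | 2 | 2 | 0 |
| Day 13 | 44 | 6 | 6 | 3 | 1 | 1 | 1 | not scheduled |
| Day 57 | 0 | 0 | 0 | 0 | 0 | 0 | 0 | not scheduled |

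The ECG columns differ because the table row and the footnote disagree. PK has a similar conflict: footnote k ends at Day 16, while the table row appears to mark samples through Day 57. The IgG, ADA and visit counts do not depend on either conflict.

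**Step 4: what a Withdrawal Visit recovers.** If attended, it gives one Total IgG, one ADA sample, one ECG and one set of safety laboratory tests, plus the other assessments in the follow-up/withdrawal column. A Day 5 trigger then gives up 9 − 1 = 8 IgG samples and 4 − 1 = 3 ADA samples. For UP0060, Protocol 2.2 describes vaccine-specific IgG that tracked total IgG, was lowest around Day 10 and was near Baseline by Day 57. Scheduled data ending on Day 5 would stop before that low point. A Day 13 trigger falls after it.

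**Step 5: weight and likelihood.** One active participant is 1/6 = 17% of a cohort's active group and 1/12 = 8% of a method's. The documents give no event rate. Exclusion criterion 21 sets QTcF limits of 450 msec for men and, in its words, "female study participants with QTcF >470msec". From those limits, crossing 500 needs a rise of more than 500 − 450 = 50 msec or 500 − 470 = 30 msec. From lower values it needs a larger rise, or a change above 60 msec.

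**The case against.** The strongest reply is that the safety signal is not abandoned. Protocol 7.1.3 requires a new clinically significant ECG finding to be reported as an AE. Section 8.3 keeps the investigator responsible for AEs that led to discontinuation, and Appendix 3 requires follow-up to resolution or stability with supplemental evaluations as medically indicated. SAEs are collected to 30 days after the end of study for each participant. This stands. A reader might infer from the withdrawal wording that a participant with a prolonged QTcF goes unmonitored, and the documents do not support that.

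A reader might also infer that the protocol otherwise always keeps dosed participants in follow-up, so that 7.1.3 is an outright contradiction. That goes too far. Section 6.7.1 keeps dosed participants in after a dosing halt, but PK and PD sampling is then conditional. Appendix 6 delays withdrawal in liver cases until the work-up is complete and does not forbid it. Sections 7.2 and 8.3.5 withdraw dosed participants for pregnancy and interfering illness, among other reasons. Retention is one pattern in the protocol, not a rule.

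Releasing a healthy volunteer with a marked QTc change from research procedures is a defensible instinct, and replacement is possible under 7.2. A replacement cannot supply this participant's own course, however, and the discretion paragraph is not written as an exception to the two limits. As worded, an investigator has one mandatory and one discretionary instruction for the same ECG.

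**Conclusion.** The point holds for triggers on scheduled post-dose ECGs. Following 7.1.3 as written spares no exposure and ends scheduled follow-up. At Day 5 the cost is all 9 ambulatory visits, 9 of 13 Total IgG samples and all 4 post-dose ADA samples, less one set if the Withdrawal Visit is attended. The two later ECGs are lost only on the table-row reading.

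The loss is mainly PD, ADA and PK data and routine detection of other non-serious TEAEs. It should not be read as material damage to the primary endpoint: if the trigger is reported as an AE the participant already counts in overall TEAE incidence, and the SAP has no hypothesis test. Nor is the rule without purpose, since on the predose ECG it can prevent the only dose.

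The conclusion assumes a single Day 1 administration that ends before 4 h. The event is probably rare, but no rate is given. The change is worth making because it is specific and cheap.

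**What to change.** Replace the withdrawal consequence in 7.1.3 with wording along these lines: *If either limit is met predose, do not dose. If met after the start of dosing, stop any ongoing infusion, repeat the ECG and follow until resolution, and continue scheduled visits to Day 57 unless consent is withdrawn or the investigator judges continuation unsafe.* State that the discretion paragraph otherwise covers findings below the two limits, and align the cross-reference in 8.2.3. For the predose check, take the change against the Screening or Day -1 ECG, because the predose reading would itself become Baseline.

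The cost is protocol wording and a few repeat ECGs in a rare case. The real downside is that a healthy volunteer with a QTc signal stays in visits that were already scheduled. The consent and investigator-judgment exceptions limit that. The wording goes somewhat further towards retention than 6.7.1 or Appendix 6.

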## 7.2 Participant discontinuation/withdrawal from the study

Participants are free to withdraw from the study at any time, without prejudice to their continued care. The study is designed to collect data on 24 participants that receive rozanolixizumab (6 per cohort). If study participants discontinue before the end of the safety evaluation period, replacement participants may be considered at the discretion of the sponsor, depending on how the discontinuation affects the study's ability to collect sufficient data to support the study

objectives. For each case of participant discontinuation, the decision on whether to recruit a replacement and the reason behind the decision will be documented.

If the participant withdraws consent for disclosure of future information, the sponsor may retain and continue to use any data collected before such a withdrawal of consent.

If a participant withdraws from the study, he/she may request destruction of any samples taken and not tested, and the investigator must document this in the site study records. Participants who withdraw from the study will be encouraged to return to the clinic to complete the Withdrawal Visit (see [Table 1-1](#)).

See [Table 1-1](#) for data to be collected at the time of study discontinuation and follow-up and for any further evaluations that need to be completed.

Participants should be withdrawn from the study if any of the following events occur:

1. Participant develops an illness that would interfere with his/her continued participation.
2. Participant is noncompliant with the study procedures or medications in the opinion of the investigator.
3. Participant takes prohibited concomitant medications as defined in this protocol that might interfere with the outcome of the study or might be an increased risk to the study participant.
4. Participant withdraws his/her consent.
5. There is confirmation of a pregnancy during the study, as evidenced by a positive pregnancy test.
6. The sponsor or a regulatory agency requests withdrawal of the participant.

